#### Patients who have received the investigational arm (Avelumab) of the POLEM trial:

- All SAEs occurring from the day of first infusion of IMP (Avelumab) until 90 days after the last infusion of IMP should be captured in the patients' medical records.
- Investigators should notify the MRC CTU at UCL (UK) and Gastrointestinal (GI) Unit Clinical Trial Office (CTO) at the Royal Marsden Hospital (RMH) by fax ([contact]) of all SAEs occurring within 24 hours of discovery or notification of the event. Any change of condition or other follow-up information should be faxed to the CTO office within 24 hours of the information becoming available. Events will be followed up until the event has resolved or a final outcome has been reached.

#### All adverse events considered to be serious and reactions (SARs and SUSARs):

- The Investigator must assess the causality of all serious events or reactions in relation to protocol treatment (either aspirin or Avelumab)
- If an SAE is considered possibly related to Avelumab AND the event occurs >90 days after the last dose of Avelumab, these SAEs will also be collected and reported to the RMH CTO ([contact]) within 24 hours of discovery.
- If a serious event occurs and is considered possibly related to aspirin, the MRC CTU should be notified as specified in the main protocol.
- If there is any doubt as to the possible causality of the reaction, the SAE should be reported to both CTUs (MRC and RMH).
- the assessment of expectedness will be based upon Reference Safety Information of the investigator brochure (IB) for avelumab
- The sponsor / chief investigator will be responsible for expedited reporting of all SUSARs to the relevant authorities (including the UK Medicines and Healthcare products Regulatory Agency and the responsible main research ethics committee) no later than 7 calendar days after the sponsor has first knowledge of the minimum criteria for expedited reporting for SUSARs which are fatal or life threatening, or no later than 15 days for SUSARs which are non-fatal or non-life threatening. These will be simultaneously reported to Merck Serono. Other investigators will be informed of these events by a periodic line listing.

Information on the final description and evaluation of a SAR report may not be available within the required time frames for reporting. For regulatory purposes, initial expedited reports should be submitted within the time limits as soon as the minimum following criteria are met:

- a) A suspected IMP
- b) An identifiable subject (e.g. trial subject code number),
- c) An AE assessed as serious and unexpected, and for which there is a reasonable suspected causal relationship,
- d) An identifiable reporting source,

And, when available and applicable:

- a) A unique clinical trial identification (EudraCT number or in case of non-European Community trials the sponsor's trial protocol code number)
- b) A unique case identification (i.e. sponsor's case identification number).

In case of incomplete information at the time of initial reporting, all the appropriate information for an adequate analysis of causality should be actively sought from the reporter or other available sources. Further available relevant information should be reported as follow-up reports.

In certain cases, it may be appropriate to conduct follow-up of the long-term outcome of a reaction.

For all SAEs the following attributed must be assigned by the investigator:

1. AE diagnosis or syndrome(s) - according to NCI-CTCAE version 4.0 classification. If AE diagnosis is not yet known, then signs or symptoms should be reported.

2. Severity – graded according to NCI-CTCAE version 4.0

3. Event description – include full details in medical terms and case description

4. Dates of onset and resolution – if not yet resolved then follow-up reports will be required until the event is considered resolved or stable.

5. Relatedness to the IMP - assessed by means of the question: "Is there a reasonable possibility that the event may have been caused by the IMP?" The investigator should respond to this question with either "related", "probably related" or "possibly related" for events which may be related to the IMP and are therefore SARs, and "probably unrelated" or "unrelated" for events which are not related to study treatment and are therefore only SAEs.

6. Expectedness - based upon the Reference Safety Information of the investigator brochure (IB) for Avelumab (i.e., section 6.2 of the IB).

7. Action taken - the investigator may additionally be asked to provide follow-up information, discharge summaries, and / or extracts from medical records or CRFs.

8. Outcome

The investigator is responsible for ensuring that all SAEs captured on the patients' medical records (as specified above) are reported on the CRF.

SAEs or SARs which are considered to be expected will be reported in a periodic line listing. Merck

Serono will each receive copies of all SAEs and SARs as well as a copy of the annual Drug Safety Update Reports (DSURs).

All SAEs reported to the CTU office shall be evaluated and escalated as appropriate in accordance with the RM / ICR SOP for SAE reporting. The chief investigator is also responsible for all submissions of annual reports to the RM R&D Office (the sponsor), MHRA and Ethics as indicated in the SOP.

It will be left to the investigator's clinical judgment to determine whether an SAE is related and of sufficient severity to require the patient's removal from treatment or from the study. A patient may also voluntarily withdraw from treatment due to what he or she perceives as an intolerable SAE If either of these situations arises, the patient should be strongly encouraged to undergo the end-of-study visit and be under medical supervision until symptoms cease or the condition becomes stable. If a patient is permanently withdrawn from the study because of a SAE, this information must be included in the initial or follow-up SAE Report Form as well as the end of study CRF.

For all deaths, available post-mortem reports and relevant medical reports should be faxed to the Trials Unit as soon as they are available.

#### **Reporting of targeted events:**

The following AEs are considered POLEM targeted events and should be reported to the RMH CTO (E-mail: [contact]; [contact]) on an SAE report form within 24 hours of discovery or notification of the event even if they do not otherwise fulfil criteria for seriousness:

- Myocardial infarction, cardiac failure and myocarditis
- Pneumonitis which is felt to be treatment-related
- Hepatic dysfunction or hepatitis which are felt to be treatment-related
- Enterocolitis which is felt to be IMP-related
- Endocrinopathy which is felt to be IMP-related
- Neuropathy which is felt to be IMP-related
- Nephritis which is felt to be IMP-related

#### 9B) POLEM Notification of Death

All deaths will be reported to the sponsor irrespective of whether the death is related to disease progression, the IMP, or an unrelated event. Death which is secondary to progressive disease should be reported on a death CRF but is not considered an SAE.

In Add-Aspirin, events relating to a patient primary cancer (including death), or a diagnosis of a new cancer, are required to be reported on SAE forms, however these do not need to be submitted within 24 hours of the investigator being aware the event (see section 7 of the main Add-Aspirin protocol for further details).

#### 9C). Pregnancy reporting:

The Investigator must make every effort to try and ensure that a clinical trial patient or a partner of a clinical trial patient does not become pregnant during the POLEM trial or for 12 months afterwards. This should be done as part of the consent process by explaining clearly to the patient the potential dangers of becoming pregnant and also providing each patient with information about appropriate medically approved contraception. Two forms of medically approved contraception should be used, such as:

- oral contraceptives and condom;
- intra-uterine device (IUD) and condom;
- diaphragms with spermicidal gel and condom.

Contraceptives should be used from the time the patient joins the trial, throughout the trial and for 6 months after completing standard adjuvant chemotherapy or 30 days after the last infusion of Avelumab. It should be explained to the patient that if his partner is pregnant or breast-feeding when he enters the trial, the patient should use barrier method contraception (condom plus spermicidal gel) to prevent the unborn baby or the baby being exposed to chemotherapy or the IMP. The Investigator must ensure that all patients are aware at the start of the study of the importance of reporting all pregnancies (in themselves and their partners) that occur whilst being treated with the IMP and occurring up to 12 months after the last IMP administration.

If a trial participant or a trial participant's partner does become pregnant during treatment with the IMP or within 12 months of last IMP administration, it must be reported to the Chief Investigator and the Sponsor within 1 day of the site staff becoming aware of it using the Pregnancy Notification Form (and similarly Add-Aspirin's Notable Event form).

Participants who become pregnant must be discontinued from trial treatment immediately. It is the Investigator's responsibility to obtain consent for follow-up from the patient or patient's partner. The Sponsor will follow-up all pregnancies for the pregnancy outcome via the Investigator and document on the pregnancy form.

The Investigator should offer counselling to the participant and/or the partner, and discuss the risks of continuing with the pregnancy and the possible effects on the foetus. With appropriate consent, monitoring of the participant and/or the partner and the baby should continue until the conclusion of the pregnancy. Pregnancy is not considered an AE unless a negative or consequential outcome is recorded for the mother or child/foetus. If the outcome meets the serious criteria, this would be considered an SAE and reported as such.

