All eligible patients who are randomised will receive standard fluoropyrimidine-based adjuvant chemotherapy for 12 or 24 weeks depending on the decision of the local investigator. The choice of adjuvant chemotherapy (i.e., 24 weeks of single agent fluoropyrimidine chemotherapy or 12 weeks of doublet, oxaliplatin-based chemotherapy) must be declared by the investigator at study entry before randomisation. Type of adjuvant chemotherapy (i.e., 24 weeks of single agent capecitabine or 12 weeks of capecitabine plus oxaliplatin) will be used as stratification factor alongside MMR status.

[figure not shown]
At the end of adjuvant chemotherapy, patients who are randomised to the investigational arm, will receive an additional 24 weeks of treatment with avelumab.

After completion of treatment, all subjects will be followed up for up to 7 years from the start of adjuvant chemotherapy.

Correlative biomarker analyses will be conducted as part of the translational study in tumour tissue samples from the resection specimens, tumour tissue samples from the relapsed tumour (if applicable, feasible and upon patient consent) and serial blood samples collected at study entry, during adjuvant treatment and follow-up.

[figure not shown]

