#### 3 **ELIGIBILITY**

# **3B) POLEM INCLUSION CRITERIA**

Please direct queries regarding POLEM eligibility to the GI Unit CTO at RMH. Eligible patient details should be sent to the GI Unit CTO at RMH ([contact]; [contact])

- 1. Male or female subjects aged ≥18 years
- 2. ECOG PS 0/1

3. Histologically proven, stage III (i.e., any T, N1 or N2, M0) adenocarcinoma of the colon (as defined by the presence of the inferior pole of the tumour above the peritoneal reflection - that is, at least 15 cm from the anal margin).

4. Fully surgically resected tumour with clear resection margins (i.e., >1 mm)

5. Locally confirmed defective mismatch repair (dMMR) tumour (as defined by the lack of staining on either pre-operative biopsy samples or resection specimens of at least one of the following proteins: MLH1, MSH2, MSH6, PMS2) or centrally confirmed POLE exonuclease domain mutated tumour (in subjects <50 years old with locally confirmed proficient (p)MMR tumours)

6. Absence of metastases as shown by a pre or post-operative CT scan

7. Absence of major post-operative complications or other clinical conditions that, in the opinion of the investigator, would contraindicate adjuvant chemotherapy

8. Adequate haematological function defined by absolute neutrophil count (ANC)  $\geq$ 1.5 × 10^9/L, platelet count  $\geq$ 100 × 10^9/L, and haemoglobin  $\geq$ 9 g/dL

9. Adequate hepatic function defined by a total bilirubin level  $\leq$ 1.5 × the upper limit of normal (ULN) range and AST and ALT levels  $\leq$ 2.5 × ULN

10. Adequate renal function defined by an estimated creatinine clearance  $\geq$ 30 mL/min according to the Cockcroft-Gault formula (or local institutional standard method)

11. Negative serum or urine pregnancy test at screening for women of childbearing potential

12. Fertile men and women must agree to take highly effective contraceptive precautions during, and for 6 months after the last dose of chemotherapy or for 1 month after the last dose of Avelumab

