## 8 POLEM TRIAL MEDICATION

Treatment on the investigational arm with Avelumab will only be administered at POLEM specific centres, once every 2 weeks for 24 weeks (i.e. 12 treatment cycles) after completion 12 or 24 weeks of standard fluoropyrimidine-based adjuvant chemotherapy.

Patients randomised to the control arm can be transferred back to their original Add-Aspirin cente, following adjuvant chemotherapy, for registration and ongoing randomisation into Add-Aspirin.

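### Appendix XIV section 9C sets a 12-month period for avoiding pregnancy but ends contraception, its stated means, at different times, and does not define the trial from which the 12 months run

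*Protocol*

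**What the plan says.** Three statements in Appendix XIV bear on this.

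- **Avoidance (section 9C, opening).** The investigator must make every effort so that a patient or a patient's partner "does not become pregnant during the POLEM trial or for 12 months afterwards". The next sentence says how: within the consent process, by explaining the dangers and giving information on contraception.
- **Contraception (section 9C, after the list of methods).** It runs from joining, "throughout the trial and for 6 months after completing standard adjuvant chemotherapy or 30 days after the last infusion of Avelumab".
- **Contraception (section 3B, POLEM inclusion criterion 12).** Fertile men and women must agree to precautions during treatment and then "for 6 months after the last dose of chemotherapy or for 1 month after the last dose of Avelumab".

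Section 9C sets a separate reporting window for pregnancies "occurring up to 12 months after the last IMP administration".

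Two further statements are needed to size the difference. Section 8 of the appendix gives avelumab for 24 weeks after chemotherapy, in 12 two-weekly cycles. The POLEM Trial Summary says that "all subjects will be followed up for up to 7 years from the start of adjuvant chemotherapy".

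**The concern.** Section 9C sets an aim, names contraception as the way to reach it, and then ends contraception at a different time from the aim. Someone preparing consent material or answering a participant's question from this page could give either end date and be following the text.

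What is at stake is possible fetal exposure, so this is a safety instruction and not a statistical one. The text also belongs to this protocol. Section 9C has pregnancies reported on Add-Aspirin's own Notable Event form as well as the POLEM form, and Appendix XIV places POLEM follow-up of referred patients at the Add-Aspirin centre. Under section 4.2.2, the Add-Aspirin run-in may start once avelumab or chemotherapy is complete and no later than 6 weeks afterwards, which falls inside the period on which the sentences differ.

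**Working it through.** The protocol gives no figure for the difference, so there is none to reproduce. The check is calendar arithmetic, with one month = 365.25 / 12 = 30.44 days.

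**Step 1. Which contraception rule ends last in the avelumab arm?** Those patients receive chemotherapy and then avelumab, so both limits could apply. Count from the end of chemotherapy and assume avelumab starts at once.

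- Chemotherapy rule: 6 × 30.44 = about day 183.
- Avelumab rule, last of 12 two-weekly infusions at week 22: 22 × 7 + 30 = day 184.
- Avelumab rule, counted from the end of the 24-week block: 24 × 7 + 30 = day 198.

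The avelumab rule ends last in both cases. A later start of avelumab would only move it further out, so it sets the end of contraception in that arm.

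**Step 2. The trial means the treatment period in both sentences.** Uncovered time = 12 months after treatment minus the contraception tail.

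- Avelumab arm: (365.25 − 30) / 30.44 = 11.0 months.
- Chemotherapy alone: 12 − 6 = 6 months.

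**Step 3. The trial includes the follow-up of up to 7 years in both sentences.** Contraception throughout the trial then runs to 84 months from the start of chemotherapy. The 6-month and 30-day tails have expired long before that, and avoidance runs to 84 + 12 = 96 months. Uncovered time is 12 months in either arm.

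**Step 4. Avoidance is counted from the end of the 7-year follow-up, but contraception stops at the treatment-based dates.** Uncovered time = 96 months minus the end of contraception.

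- Avelumab arm, 12 weeks of chemotherapy: contraception ends at (36 × 7 + 30) / 30.44 = 9.3 months; 96 − 9.3 = 86.7.
- Avelumab arm, 24 weeks of chemotherapy: (48 × 7 + 30) / 30.44 = 12.0; 96 − 12.0 = 84.0.
- Control arm, 12 weeks: (12 × 7) / 30.44 + 6 = 8.8; 96 − 8.8 = 87.2.
- Control arm, 24 weeks: (24 × 7) / 30.44 + 6 = 11.5; 96 − 11.5 = 84.5.

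This gives about 84 to 87 months. It is an extreme that nobody is likely to intend, but the wording does not exclude it.

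**Step 5. Does the reporting window explain the 12 months?** No. It is stated separately and tied to the last dose of the investigational product. The opening sentence concerns preventing pregnancy, and ties its 12 months to the trial.

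**The case against.** The strongest reply is that the contraception instruction is itself consistent. Section 9C and criterion 12 agree (6 months, and 30 days or 1 month), and only one introductory sentence differs, worded as a best-effort duty on the investigator. That is fair as far as it goes. Criterion 12 does not conflict with the contraception sentence, and the contradiction lies between both of these and the avoidance sentence. It remains a contradiction, because the avoidance sentence names contraception as its means.

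A second reply rests on the requirement to use contraception throughout the trial. If that phrase covers the 7-year follow-up while the 12 months are counted from the end of treatment, contraception outlasts avoidance and nothing is uncovered. This gives one word two meanings in one section and leaves the 6-month and 30-day limits with no function. Criterion 12, which does not contain the phrase, would still stop 11 or 6 months short.

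Third, the main protocol protects some participants. Section 3.4, exclusion 17, excludes those who are pregnant or intend pregnancy during Add-Aspirin treatment, and section 5.4.4 advises against pregnancy in that period. This stands for women who enter Add-Aspirin. It does not reach partners of male participants, whom section 9C includes, or POLEM patients who never enter Add-Aspirin.

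Three stronger inferences are tempting, and the document does not support them:

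- **That the protocol states an 11-month gap.** The figure depends on taking the undefined trial to end at the last dose.
- **That 402 patients are affected.** That is the whole planned POLEM sample. The 11-month figure could concern only the avelumab arm (201 planned), and the appendix is largely aimed at patients referred from Add-Aspirin centres. Neither the number referred nor the fertile fraction is given.
- **That Add-Aspirin centres counsel participants on contraception in this window and will give conflicting advice.** Section 9C places the counselling in the consent process, and section 2 of the appendix has the POLEM centre take consent. The extra follow-up assessments in section 6 do not include contraception.

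**Conclusion.** The point holds as an internal contradiction in a safety instruction. The avoidance period and the contraception period in section 9C do not end together, criterion 12 repeats the shorter contraception periods, and the reference point for the 12 months is undefined.

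If the trial means the treatment period, the difference is about 11 months in the avelumab arm and 6 months after chemotherapy alone. If it includes the 7-year follow-up in both sentences, 12 months are uncovered. Whenever the word keeps one meaning in the two sentences, part of the avoidance period has no contraception rule.

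The number of participants affected cannot be derived. The point is minor for Add-Aspirin as a trial, since it changes no endpoint, sample size, randomisation or analysis. It takes no position on which period is right.

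**What to change.** Reconcile the avoidance and contraception sentences of Appendix XIV section 9C with each other and with POLEM inclusion criterion 12 in section 3B. For each arm, both periods should count from one defined event and finish at one stated time, and the text should say whether the trial means treatment or treatment plus follow-up. If a difference between the two periods is intended, the text should say so and give the reason.

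The POLEM sponsor must confirm the periods, because the Add-Aspirin team cannot settle them alone. The reporting window can stay separate.

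The cost is about one sentence in the appendix, a check against the POLEM protocol, and matching participant information.

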# 10 POLEM STUDY SUMMARY

SUMMARY INFORMATION TYPE	SUMMARY DETAILS		
Study trial	Avelumab plus fluoropyrimidine-based chemotherapy as adjuvant treatment for stage III dMMR or POLE exonuclease domain mutant colon cancer: A phase III open label randomised study.		
Study number and acronym	CCR4673-POLEM		
EudraCT #	2017000370-10		
NRES No.	18/LO/0165		
Planned number of patients	402 patients will be enrolled		
Planned treatment duration per subject	Patients will be randomised in a 1:1 ratio to receive standard 12 or 24 weeks of fluoropyrimidine-based adjuvant chemotherapy (i.e., either 4 cycles of CAPOX or 8 cycles of single agent Capecitabine based on local investigator's decision) or fluoropyrimidine based chemotherapy followed by 24 weeks of Avelumab.		
Study Objective	To demonstrate that administering Avelumab after standard adjuvant fluoropyrimidine-based chemotherapy improves the rate of 3-year disease free survival (DFS) compared with standard fluoropyrimidine-based adjuvant chemotherapy alone in stage III dMMR or POLE exonuclease domain mutant colon cancer		
Primary Outcome Measure	3-year DFS - defined as the proportion of subjects who are alive and free of disease 3 years after randomisation		
Secondary Objectives and Outcome Measures	
 
To evaluate overall survival (OS) at 5 and 7 years by treatment arm
 
To evaluate survival outcomes (including DFS and OS) by predefined clinical, pathological and molecular factors         
 
Subgroups analyses will be performed by POLE status, MMR status, age, gender, tumour location, type of adjuvant chemotherapy and TN stage
 
 
 
The safety profile/toxicity of the investigational treatment arm.
 
Health-related quality of life (HRQoL) assessed using the EORTC QLQ C-30 and the EuroQol EQ-5D-5L questionnaires
 
The cost effectiveness of adjuvant treatment by treatment arm assessed by Quality Adjusted Life Years (QALYs) and Health Resource Use
 
		
Exploratory / Translational	To evaluate predictive factors of clinical benefit and safety of Avelumab in tumour tissue and blood samples. Molecular studies will be performed on primary tumour tissues (resected specimens) and blood samples. If applicable, analyses will be extended to tumour tissues from the site of relapse.		

SUMMARY INFORMATION TYPE	SUMMARY DETAILS	
Investigational therapy: product / dosing schedule / mode of administration	Avelumab will be administered once every 2 weeks intravenously at the dose of 10mg/kg body weight for 12 cycles.	
Follow up duration	7 years (from the start of adjuvant chemotherapy)	
Planned date for primary analysis:	End of September 2025	
Planned date for analyses of follow-up phase data:	End of September 2029	
Planned Trial Period	10 years	
Sample size calculation	The primary endpoint is DFS at 3 years. The 3-year DFS rate in the control arm is expected to be about 75% (72). The experimental treatment (fluoropyrimidine-based chemotherapy followed by Avelumab) is expected to improve the 3-year DFS rate by 12% (to 87%), corresponding to a hazard ratio (HR) of 0.48. This effect size is justifiable since the population is highly enriched (with dMMR and POLE mutant patients) and secondly, a large effect size will also allow potential for cost- effectiveness of the experimental intervention. Therefore, a sample size of at least 171 per group (342 in total) is required (60 DFS events in total) to reject the null hypothesis of: H 0 ; HR =1 vs H 1 : HR HR $\neq$ 1 with at least 80% power assuming a two sided 5% type I error. Assuming further a 15% dropout rate (loss to follow up rate) a total sample size of 402 will be required (201 per group in a 1:1 randomisation).	
Co-Sponsors		
Funders	Merck Serono Financial support: Grant to support study Non-financial support: IMP and labelling	

